7.1.2 Descriptive analyses

The SRI-4 response status, patients who successfully achieve steroid tapering, SRI-4 response status with sustained steroid reduction (primary variable) at Week 29 will be summarized by treatment. Descriptive statistics will include frequency and percentage.

7.1.3 Statistical model, assumptions and hypotheses

The primary endpoint will be analyzed using a Bayesian logistic regression model. The model will include treatment group, ENA status, baseline SLEDAI-2K (<10 , ≥ 10) as fixed effects. Weakly informative prior will be used to obtain the posterior estimates. The primary analysis will be performed for each cohort separately.

Bayesian posterior probabilities will be used to assess the following criteria as a guide for decision making ([Fisch et al 2015](#)).

Efficacy criteria (for primary endpoint):

- Week 29 responder rate in active group better than that in placebo group with high confidence (90%), i.e., $\text{Prob}(\theta_{\text{active}} - \theta_{\text{placebo}} > 0) > 90\%$, AND
- Average magnitude of effect on Week 29 responder rate $> 15\%$ over placebo, i.e., $\text{Prob}(\theta_{\text{active}} - \theta_{\text{placebo}} > 15\%) > 50\%$.

Where θ is the Week 29 responder rate, i.e. the proportion of responders per definition.

The 15% threshold is chosen based on a study showing around 15% difference in responder rate based on SRI-4 with sustained reduction in oral corticosteroid at Week 24 between an active treatment and placebo ([Furie et al 2017](#)).

Futility criterion:

- Week 29 responder rate in active group worse than that in placebo with confidence higher than 60%, i.e., $\text{Prob}(\theta_{\text{active}} - \theta_{\text{placebo}} < 0) > 60\%$.

The posterior estimates of the treatment effect of VAY736 and CFZ533 compared to their matching placebos (along with the 90% credible intervals) at Week 29 will be provided. The results will be reported in terms of difference in probability of responders.

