5.1 Inclusion criteria

Subjects eligible for inclusion in this study must meet **all** of the following criteria:

1. Written informed consent must be obtained before any assessment is performed
2. Male and female patients 18 to 75 years of age
3. Fulfill ≥ 4 of the 11 American College of Rheumatology 1997 classification criteria for SLE ([Hochberg 1997](#); [Tan et al 1982](#)) at screening
4. Patient diagnosed with SLE for at least 6 months prior to screening
5. Elevated serum titers at screening of ANA ($\geq 1:80$) of a pattern consistent with an SLE diagnosis, including at a minimum either anti-double stranded DNA (anti-ds DNA) or anti-Ro (SSA) or anti-La (SSB) or anti-nuclear ribonucleoprotein (anti-RNP) or anti-Smith (anti-Sm)
6. Currently receiving corticosteroids and/or anti-malarial and/or thalidomide treatment and/or another DMARD **CCI**

7. SLEDAI-2K score of ≥ 6 ([Gladman et al 2002](#)) at screening

8. BILAG-2004 score at screening of:
 - at least one “A” in either the mucocutaneous domain or in the musculoskeletal domain,
OR
 - one “B” in either the mucocutaneous or musculoskeletal domain AND at least one “A” or “B” in a second domain ([Isenberg et al 2005](#), [Isenberg et al 2011](#), [Yee et al 2006](#), [Yee et al 2010](#))
9. Able to communicate well with the investigator, to understand and comply with the requirements of the study
10. Weigh at least 40 kg at screening

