6.2.2 Permitted concomitant therapy requiring action (guided CS tapering)

Corticosteroids. Patients on stable, maintenance dosing of oral corticosteroids (≤ 30 mg/day prednisone or equivalent) prior to randomization should continue this dosing level until Week 5. From Week 5 visit onwards, patients will undergo a guided CS dose reduction from baseline levels according to the following schedule:

- Achieve by Week 17 a prednisone dose or equivalent of ≤ 5 mg/day or less than CS dose at Baseline, whichever dose is lower.
- Any remaining corticosteroid dosing at Week 17 should subsequently be kept stable up to the Week 29 visit.
- Patients who are unable to reach these reduced CS dose level goals by week 17 or maintain these achieved CS dose levels through to Week 29 will be considered a non-responder for primary endpoint.
- Limited adjustments in CS dosing after Week 17 are provided (see [Section 6.2.4](#) Rescue medication and [Table 6-3](#) Prohibited medication).
- Further adjustments of corticosteroids and of other DMARD co-medications may take place during the open label period after Week 29 according to PI discretion.

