6.3.2 Treatment assignment, randomization

Randomization has to be performed via the IRT system at the Baseline visit at the latest. All eligible participants will be randomized to one of the available treatment arms using the IRT system. The Investigator or his/her delegate will contact the IRT system after confirming that the participant satisfies all the inclusion/exclusion criteria. The IRT system will specify a unique medication number for the package of investigational drug to the participant. The randomization number will not be communicated to the requester.

The randomization scheme for participants will be reviewed and approved by a member of the Novartis Randomization Office.

If study participants are only eligible for VAY736 Cohort (i.e., meeting exclusion criterion 1), they will be randomized to either active arm or placebo arm of Cohort 1. Otherwise, the participants will be randomized to one of four treatment arms of two cohorts.

Randomization will be stratified by ENA status (positive vs. negative) and SLEDAI-2K <10, ≥10 status at Baseline, based on screening results, in order to remove any possible confounding impact on treatment effects.

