12.2 Subject demographics and other baseline characteristics

Demographic and baseline characteristics (e.g., SLEDAI-2K, BILAG-2004, Physician Global Assessment, Patient Global Assessment, CCI [REDACTED] and baseline steroid dose) will be listed by subject and summarized by treatment group. Categorical data will be presented as frequencies and percentages. For continuous data, mean, standard deviation, median, minimum and maximum will be presented.

Relevant medical histories and current medical conditions at baseline will be summarized separately by system organ class and preferred term, and by treatment group. They will also be listed by subject and treatment group.

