On the baseline visit Day 1, following patient eligibility confirmation and completion of all assessments, first dose of study drug/placebo will be administered. The last treatment in the blinded treatment period will be given at the Week 25 visit. The readout for the blinded treatment period will be performed at Week 29. Study drug will be administered every 4 weeks. Unless otherwise stated, all assessments must be completed BEFORE the next dose of study drug is administered.

Guided corticosteroid (CS) reduction

- Patients entering the study on a stable CS regimen are required to undergo a guided CS taper from baseline levels starting at Week 5 in order to achieve by Week 17:
 - a daily CS dose of ≤ 5 mg/day prednisone or equivalent,
 - or a CS dose that is less than the baseline dose, whichever is the lower dose.
- In addition, the patient should remain at the lowered CS dose achieved at Week 17 through to Week 29.
- Patients entering the study without background CS therapy should remain free of any CS regimen or increase in SoC DMARDs through to week 29.

- Patients exceeding the rescue therapy allowances may continue in trial but will be labeled a non-responder for primary endpoint.
- During the open label phase, further reductions in patients' SoC CS and DMARDs may be made on an individual basis as deemed appropriate by the investigator.

Open-label treatment phase

At the end of the Week 29 visit, after all assessments have been performed, the first open label treatment will be administered. Patients in Cohort 1 will receive VAY736 and patients in Cohort 2 will receive CFZ533. Study drug will be administered every 4 weeks. The last treatment will be given at the Week 49 visit, and the End-of-Treatment (EoT) visit will be performed 4 weeks thereafter, at Week 53.

Follow-Up period

After completion of the open-label treatment period, all patients will enter a Follow-Up period in order to monitor safety and efficacy up to Week 69. The Week 69 visit is the End of Study (EoS) visit for patients in Cohort 2 (CFZ533). The study duration for patients in Cohort 2 will be approximately 18 months.

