7.1.1 Variables

The primary endpoint is a composite of SRI-4 response at Week 29 with sustained reduction in oral corticosteroid from Week 17 through Week 29.

SRI-4 response is defined as below:

- having ≥ 4 points reduction from baseline in SLEDAI-2K score AND
- no new BILAG-2004 A organ domain score and no more than one new BILAG-2004 B organ domain scores compared with baseline AND
- < 0.3 mm or < 10 mm point increase if scaled 0 to 3 or 0 to 100 mm, respectively in the physician's global assessment from baseline

Sustained reduction in oral corticosteroids is defined as below:

- ≤ 5 mg/day or \leq baseline dose, whichever is lower, at Week 17
AND
- no increase of that dose from Week 17 through Week 29

When all these criteria are met, the patient is considered as a responder. However, patients receiving CS dosing in addition to the baseline CS dosing levels or subsequent, reduced levels attained at Week 17 after completing the guided corticosteroid tapering period will be considered non-responder for primary endpoint:

- if total daily CS dose is > 30 mg/d prednisone or equivalent, or
- increased daily CS dose is administered > 2 days within a 4-week treatment cycle, or
- daily CS dose is increased within 2 weeks of Study Visit Week 29.

Patients who have taken other rescue medication or prohibited medication (Table 6-3 of study protocol, e.g., new immune suppressive agents or biologics) or drop out before Week 29 will also be considered non-responder for the primary endpoint. Where acute CS administration occurs for purposes other than the treatment of SLE disease activity, patient responder status will be discussed on a case-by-case basis.

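### The primary responder model omits baseline corticosteroid dose, although one of the two joint response conditions is defined against that dose

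*SAP*

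**What the plan says.** The primary model is the same in protocol 12.4.2 and SAP 7.1.3: "The model will include treatment group, ENA status, baseline SLEDAI-2K", the last split at 10. These are also the randomisation strata; protocol 6.3.2 states "Randomization will be stratified by ENA status (positive vs. negative") together with the same SLEDAI-2K cut. Neither list contains steroid dose.

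The endpoint does depend on steroid dose. SAP 7.1.1 says: "The primary endpoint is a composite of SRI-4 response at Week 29 with sustained reduction in oral corticosteroid". The steroid condition is at most 5 mg/day or at most the "baseline dose, whichever is lower, at Week 17", with no increase to Week 29 beyond limited allowances. Some patients enter on no steroid (SAP 1.4: "Patients entering the study without background CS therapy should remain free of any CS regimen"). Others may enter on up to 30 mg/day (protocol 6.2.2).

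The dose is already held: protocol 12.2 names baseline characteristics to be listed and summarised by arm, among them SLEDAI-2K, BILAG-2004 "and baseline steroid dose".

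One wording difference affects how baseline dose drives response. The taper text (protocol sections 3 and 6.2.2, SAP 1.4) asks for less than the baseline dose, while the endpoint definitions (protocol 12.4.1, SAP 7.1.1) accept a dose equal to it. These passages must be reconciled.

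**The concern.** A patient entering on 30 mg/day has further to taper than one entering on 5 mg/day, and failing the taper makes the patient a non-responder whatever happens to SRI-4. Baseline dose is therefore a plausible predictor of response by construction. The SAP follows this logic elsewhere: the models for the physician's and patient's global assessments (SAP 7.2.3) include the baseline value of the outcome as a continuous covariate. The primary model has no counterpart for steroid dose.

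At stake is the per-cohort decision, which rests on a posterior difference judged against 0 and 15 percentage points. With 30 per arm and no stratification on dose, the arms can differ in starting dose by chance, and the planned model cannot separate that difference from a drug effect.

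**Working it through.** **Inputs from the documents.** 30 per arm; 17% versus 17 + 25 = 42% responders; 84% chance of meeting both criteria, about 10% under no effect (protocol 12.8.1). Criteria: P(difference > 0) > 90% and P(difference > 15 points) > 50% (SAP 7.1.3). Entry dose 0 to 30 mg/day.

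**Inputs assumed, because the documents give none.** 20% of patients on no steroid; mean dose 8.7 mg/day, SD about 7.7, capped at 30; coefficient priors normal with SD 2.5; a range of prognostic strengths. An odds ratio (OR) per 10 mg converts to log-odds per SD as ln(OR) × 0.77, so OR 0.6, 0.4 and 0.2 give -0.39, -0.71 and -1.24.

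**Step 1: the plan's own figure.** Exact binomial enumeration with flat or weak beta priors gives 81.1 to 81.2% for both criteria, against the stated 84%. Under no effect it gives 6.0% for both criteria and 9.6 to 10.8% for the first alone. A placebo prior centred at 17% and worth 10 patients gives 86%, so an unpublished prior could explain the gap. This does not affect the present point: the steps below compare two models under one prior, and their absolute level (about 77%) is not a statement about the plan's power.

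**Step 2: how often imbalance occurs.** SE of the difference in mean dose = 7.7 × √(2/30) = 7.7 × 0.258 = 2.0 mg/day. A difference of at least 3 mg/day is 3/1.99 = 1.51 SE, about 13% of trials (simulated: 12 to 14%). In SD units, the chance of exceeding 0.25 is 33% and of exceeding 0.5 is 5%.

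**Step 3: how far it moves the estimate.** To first order the shift is p(1 − p) × |ln OR|/10 × imbalance. For OR 0.6 and 2 mg/day: 0.17 × 0.83 × 0.0511 × 2 = 1.4 points. The calculated shifts, in percentage points, are:

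| OR per 10 mg | 2 mg/day (1 SE) | 4 mg/day (2 SE) |
|---|---|---|
| 0.8 | 0.6 | 1.3 |
| 0.6 | 1.5 | 3.0 |
| 0.4 | 2.6 | 5.5 |
| 0.2 | 4.4 | 9.5 |

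**Step 4: precision.** Posterior SD of the standardised risk difference, planned model versus planned model plus dose (2,500 to 3,000 simulated trials per scenario):

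| Scenario | Planned | With dose | Variance reduction, 1 − (ratio)² |
|---|---|---|---|
| Not prognostic | 0.105 | 0.104 | none lost |
| OR 0.6 | 0.105 | 0.103 | 4% |
| OR 0.4 | 0.105 | 0.101 | 7% |
| OR 0.2 (SLEDAI-2K also prognostic) | 0.105 | 0.097 | 15% |
| Taper success 95% at ≤5 mg, 40% above | 0.1049 | 0.1017 | 6% |

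The last row makes SRI-4 independent of dose and lets dose act only through the taper. A separate simulation (1,500 trials per scenario) gave about 4%, 8% and 15% at log-odds -0.5, -0.8 and -1.1 per SD.

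**Step 5: the decision when arms are imbalanced.** Chance of meeting both criteria at 17% versus 42%, when the active arm starts lower / higher by at least 3 mg/day (2,500 trials per scenario; about 150 to 185 trials per cell, SE 2 to 4 points):

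| OR per 10 mg | Planned model | With dose |
|---|---|---|
| 0.6 | 91% / 67% | 79% / 73% |
| 0.4 | 90% / 55% | 75% / 68% |
| 0.2 | 90% / 53% | 78% / 76% |

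The gap falls from 24, 35 and 37 points to 6, 7 and 2. The separate simulation, at -0.8 per SD and marked imbalance, gave 87%/65% and 77%/77%. With no true effect and OR 0.4, a favourable imbalance led to a false go in 9% of trials (planned) versus 4% (with dose). The two models reached different decisions in 5 to 9% of all trials.

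**Step 6: average over all trials.** The chance of meeting both criteria changed by 0 to +2 points in the separate simulation, and by between -1 and +2 points across all runs that added only dose. With dose not prognostic it was 77% under both models.

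**The case against.** The model adjusts for exactly the stratification factors, identically in both documents. The study is described as non-confirmatory and its criteria as a guide, so further covariates can be called a preference. Chance imbalance is random error, already reflected in the posterior spread. Baseline dose and the separate response components are tabulated by arm, so an imbalance would be visible. With 30 × 0.17 + 30 × 0.42 = 17.7 expected responders per cohort, and about half that at the first interim, there is little room for extra terms. SAP 7.1.3.1 shows only a heading in the public copy, so a steroid-adjusted supportive analysis may already exist.

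Much of this stands. Four stronger readings are tempting and should not be drawn:

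- **That the omission biases the result.** Allocation is randomised, so it does not.
- **That adjustment raises the chance of success.** The first criterion alone can gain about 1 to 3 points, in runs of a larger model that also made SLEDAI-2K continuous and flagged 0 mg. The plan requires both criteria, and on both the average barely moves.
- **That the SLEDAI-2K split is an equal fault, or that ENA is uninformative.** The SLEDAI-2K class is both stratified and modelled, and a continuous score gains only 1 to 2% of the SD. The share of ENA-negative patients is not given, and protocol 4.1 gives a reason for stratifying on ENA.
- **That patients on no steroid pass the taper automatically.** They must stay free of steroids to Week 29, within the rescue limits.

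The shortage of responders argues against a larger model, not against one term. The larger model just mentioned lowered the chance of meeting both criteria from 79.2% to 76.8% when neither covariate was prognostic. Adding dose alone showed no such loss. Tabulating an imbalance reveals it but leaves the decision probabilities unadjusted.

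**Conclusion.** The point holds as a correctable weakness, not an error that invalidates the analysis. The primary model omits a covariate that is already collected and against which one of the two joint response conditions is defined. The main gain is a decision that depends much less on which arm happens to start on lower doses; the 4 to 15% reduction in variance is secondary.

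These sizes rest on the assumed dose distribution, priors and prognostic strengths. If dose predicts response only weakly, the benefit shrinks towards zero, and the cost is negligible. The difference between the recomputed 81% and the stated 84% is a separate matter.

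**What to change.** In protocol 12.4.2 and SAP 7.1.3:

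1. Keep treatment, ENA status and the SLEDAI-2K class, so that the model still matches the randomisation.
2. Add baseline prednisone-equivalent dose (mg/day) as one continuous covariate under the same weakly informative priors, with no further terms.
3. Report the difference in responder probability standardised over the cohort's covariates.
4. Keep the current model as a sensitivity analysis.

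If the unseen SAP 7.1.3.1 already contains a dose-adjusted analysis, the remaining question is which model leads. SAP section 5 says that final CFZ533 results have already been reported. Wherever Week 29 data have been unblinded, the adjusted result should be labelled as a later, supportive analysis.

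The cost is a change of wording and one coefficient on data already held. In simulation, precision was not lost when dose was unrelated to response.

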7.1.3.1 Supportive analysis

7.2 Secondary objectives

7.2.1 Variables

The secondary variables are:

- Physician's global assessment (PhGA) in VAS
- Patient's global assessment (PGA) in VAS
- Flare: flare determined by BILAG-2004 as below
 - Severe flare: developing a BILAG-2004 "A" score in any system due to items that are new or worse
 - Moderate flare: having two or more "B" scores due to items that are new or worse

7.2.2 Descriptive analyses

Physician's global assessment (PhGA) in VAS and the change from baseline will be summarized by period, treatment and visit. Summary statistics will include mean, SD, median, minimum and maximum. Patient's global assessment (PGA) in VAS will be analyzed in the same way as physician's global assessment (PhGA) in VAS.

The proportion of patients with moderate flare, severe flare, and combined moderate or severe flare will be summarized by period and treatment. The time to first moderate or severe flare will be summarized for blinded, open-label and follow-up period by treatment group. Flares will be listed by period and treatment.

7.2.3 Statistical model, assumptions and hypotheses

Bayesian mixed effect model for repeated measure (MMRM) will be applied to the change from baseline in Physician's global assessment (PhGA) in VAS, as continuous response variable. The model will include treatment group, ENA status, baseline SLEDAI-2K (<10 , ≥ 10) and visit as fixed effects and baseline PhGA as continuous covariate. Weakly informative priors will be used to obtain the posterior estimates and unstructured covariance will be assumed. The posterior estimates of the treatment effect of VAY736 and CFZ533 compared to their matching placebos (along with the 90% credible intervals) at each visit will be provided. The results will be reported in terms of group estimate and treatment difference in PhGA in VAS. Patient's global assessment (PGA) in VAS will be analyzed in the same way as physician's global assessment (PhGA) in VAS. For both PhGA in VAS and PGA in VAS, data up to Week 29 will be used in the model.

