1.3 Study objectives

Table 1-1 Objectives and related endpoints

Objective(s)	Endpoint(s)
Primary objective(s)	Endpoint(s) for primary objective(s)

To determine the effect of VAY736 and of CFZ533 versus their respective placebo on disease activity in SLE patients at Week 29 compared to baseline	
SRI-4 response status at Week 29 with reduced steroid dose maintained between Weeks 17 and 29
Secondary objective(s)	Endpoint(s) for secondary objective(s)

To assess safety and tolerability of VAY736 and of CFZ533 in patients with SLE	
Adverse events and other safety data such as vital signs, ECG and laboratory results recorded during study

To determine the change from baseline in the Physicians' Global Assessment (PhGA) at Week 29 in VAY736-, CFZ533- or their respective placebo-treated arms	
Changes between baseline and Week 29 in the PhGA visual analog scale (VAS) assessing patient's overall disease activity

To determine the change from baseline in the Patient's Global Assessment (PGA) at Week 29 in VAY736, CFZ533 or their respective placebo-treated arms	
Changes between baseline and Week 29 in the patients' VAS assessing their global disease activity

To determine the pharmacokinetics (PK) of multiple doses of VAY736 (s.c.) and CFZ533 (i.v.) in SLE patients	
PK Cohort 1 (VAY736): free VAY736 serum concentration (C_{trough}). PK Cohort 2 (CFZ533): free CFZ533 concentration in plasma (C_{max}, C_{trough}).

To assess the effect of VAY736 and of CFZ533 versus their respective placebo to prevent disease flares in SLE patients	
Flare rate and time to first flare, with flare defined as one new 'A' score or two or more 'B' score using BILAG -2004

Objective(s)	Endpoint(s)

To evaluate the immunogenicity of multiple doses of VAY736 (s.c.) or CFZ533 (i.v.) in SLE patients	
Anti-VAY736 (Cohort 1) or anti-CFZ533 (Cohort 2) antibodies and incidence of ADA-positive patients.

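### The PhGA/PGA repeated-measures model lists treatment and visit as main effects only, which contradicts the promised per-visit treatment effects and does not target Week 29 unless the effect is constant

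*SAP*

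**What the plan says.** SAP 1.3 (Table 1-1) defines the secondary endpoint as "Changes between baseline and Week 29 in the PhGA visual analog scale (VAS) assessing patient's overall disease activity", with a parallel entry for the patient's VAS. Protocol Table 2-1 agrees.

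SAP 7.2.3 sets out the model. The list of terms begins "The model will include treatment group, ENA status, baseline SLEDAI-2K" (dichotomised at 10) and ends "and visit as fixed effects and baseline PhGA as continuous covariate". On priors and covariance it says "Weakly informative priors will be used to obtain the posterior estimates and unstructured covariance will be assumed". Data up to Week 29 enter the model, and PGA is handled in the same way as PhGA.

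The same paragraph then describes the output: the treatment effects of VAY736 and CFZ533 "compared to their matching placebos (along with the 90% credible intervals) at each visit will be provided".

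Protocol 12.5.1 gives the same list of terms and the same covariance. Neither document lists a treatment-by-visit interaction. The sentence listing the terms is complete in both, so the absence is not due to redaction.

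**The concern.** Two parts of one SAP paragraph do not fit together. A model with treatment and visit as main effects has one treatment coefficient. Fitted as listed, it would give the same active-minus-placebo difference and the same interval at every visit. That is not a set of visit-specific effects, and it equals the Week 29 effect only if the effect is already complete at Week 5 and stays constant.

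No section states or justifies a constant effect, and the design makes it doubtful. Patients hold their baseline steroid dose until Week 5, taper to Week 17, then hold the reduced dose to Week 29 (protocol 6.2.2). Protocol 4.1 explains that the taper and the period at the lower dose are placed before the assessment of the primary and key secondary outcomes. A common effect brings the Week 5 visit and the taper visits back into the Week 29 estimate.

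At stake are the Week 29 estimates and intervals for both global assessments in each cohort.

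**Working it through.** **Inputs from the documents**
- Visits in the model: Weeks 5, 9, 13, 17, 21, 25 and 29, so seven (protocol Table 8-1, PhGA and PGA rows; SAP 7.2.3 for the Week 29 cut-off).
- Patients per arm: 30 (protocol 12.8.1).
- Effect size, SD and within-patient correlation for PhGA or PGA: not given. Protocol 12.8.2 has no secondary-endpoint calculation, so there is no stated figure to reproduce. All values below for these quantities are assumptions.

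**Step 1: what the listed terms imply.** For patient i at visit j, with A = 1 for active,

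E(change) = m + τ·A(i) + v(j) + ENA term + SLEDAI-2K term + β·baseline.

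Active minus placebo at visit j is τ for every j. The unstructured covariance describes the residuals and does not free the mean difference to vary by visit.

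**Step 2: what τ estimates.** With complete data and priors weak enough to ignore, the estimate is w′d. Here d holds the seven visit differences and w = S⁻¹1 / (1′S⁻¹1), where S is the covariance matrix.
- Compound symmetry (CS), equal variances: every weight is 1/7 = 0.143.
- AR(1) 0.7: 0.286 on Weeks 5 and 29, 0.086 on each of the other five.
- AR(1) 0.9: 0.40 on Weeks 5 and 29, 0.04 on each of the other five.

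The common effect is therefore a covariance-weighted combination, and a plain average only in the first case.

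**Step 3: share of the true Week 29 effect recovered, equal variances**

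| Assumed effect profile | CS 0.5 or 0.7 | AR(1) 0.7 | AR(1) 0.9 |
|---|---|---|---|
| Constant from Week 5 | 1.00 | 1.00 | 1.00 |
| Linear rise from Week 1, plateau at Week 13 | 0.86 | 0.78 | 0.72 |
| Linear rise from Week 1 to Week 29 | 0.57 | 0.57 | 0.57 |
| Linear rise starting after Week 13 | 0.36 | 0.41 | 0.46 |

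Worked entries:
- Linear, CS: (4+8+12+16+20+24+28)/28 = 4, and 4/7 = 0.57.
- Plateau, CS: (1/3 + 2/3 + 5)/7 = 0.86.
- Late start, CS: (0.25+0.50+0.75+1)/7 = 0.36.
- Late start, AR(1) 0.9: 0.04 × 1.5 + 0.40 × 1 = 0.46.

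The direction can reverse. If the effect fell linearly from twice the Week 29 value at Week 5, the CS result is (2.00+1.83+1.67+1.50+1.33+1.17+1.00)/7 = 1.50, an overstatement by half.

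**Step 4: unequal variances, linear rise**
- SD growing from 14 to 24 mm, AR(1) 0.7: about 37% recovered.
- SD shrinking from 24 to 14 mm, AR(1) 0.7: 77%.
- SD growing by 60%, CS 0.6: the Week 29 weight is −0.12 and 12% is recovered.

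The equal-variance figures are therefore not bounds.

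**Step 5: width of the interval.** The ratio of the common-effect SE to the Week 29 SE is √[1/(1′S⁻¹1)] divided by the Week 29 SD. For CS 0.5 this is √[(1 + 6×0.5)/7] = 0.76, and for CS 0.7 it is √[(1 + 6×0.7)/7] = 0.86. AR(1) 0.7 gives 0.70 and AR(1) 0.9 gives 0.87. The range is 0.70-0.87.

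**Step 6: check by simulation.** 400 trials were simulated with 30 per arm, SD 20 mm, CS 0.5 and an effect growing linearly to −10 mm at Week 29, fitted with an unstructured covariance. The listed terms gave a mean estimate of −5.6 mm at every visit (empirical SE 4.4). With the interaction, the Week 29 mean was −10.1 mm (empirical SE 5.3).

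**The case against.** The strongest reply is that the per-visit promise shows the interaction was intended and merely left out of the list, since identical estimates repeated at seven visits would serve no purpose. That may be so, but the text does not settle it. An analyst must either fit the listed terms and fail to deliver visit-specific effects, or fit a term that the plan does not contain.

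A reader might infer from the list that the SAP plans to report one all-visit average. It does not: no sentence says so, and the output sentence says the opposite. It would also be too strong to say that the model can give no Week 29 figure. It gives one, on a constant-effect assumption.

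A reader might also infer that Week 29 efficacy will be understated. That requires a growing effect, which the documents do not establish. Protocol 1.1.2 describes rapid B-cell depletion and early improvement after single infusions in Sjögren's syndrome, and protocol 4.3 mentions a loading regimen. These do not show a constant effect in SLE, but they prevent treating slow build-up as given.

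The plan also contains by-visit descriptive summaries (SAP 7.2.2) and plots to Week 29 (SAP 7.2.3.2), so the raw Week 29 difference will be visible. Those are unadjusted and do not replace the model estimate. The model-checking text in SAP 7.2.3.1 is not visible and cannot be judged.

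Finally, the visible decision criteria (SAP 7.1.3) use only the primary responder rate. This stands and limits the severity.

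**Conclusion.** Wrong as written, moderate severity. The listed fixed effects contradict the SAP's promised per-visit effects and match the Week 29 endpoint only under a constant effect that no section supports. This follows from the algebra and needs no assumed inputs.

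The numerical consequence does depend on assumptions. With equal variances, recovery runs from 100% (constant effect) to 36-46% (effect starting only after Week 13). Changing variances can move it either way, and a waning effect is overstated. No single bias figure should be quoted for this trial. With equal variances the interval is also too narrow for a Week 29 effect, with an SE about 0.70-0.87 of the correct one.

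The severity is held down because PhGA and PGA are secondary endpoints in a study described as non-confirmatory (SAP 1.4).

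**What to change.** In SAP 7.2.3, add the treatment-by-visit interaction to the fixed effects for PhGA and PGA. State that each model uses its own baseline score as covariate, keep the unstructured covariance, and name the Week 29 active-minus-placebo contrast with its 90% credible interval as the secondary-endpoint estimate. A baseline-by-visit term is optional. Its absence contradicts nothing in the documents.

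Protocol 12.5.1 can be aligned at the next amendment. Protocol 12.5 leaves the details of secondary-endpoint methods to the SAP, so an amendment for this alone is not needed.

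The cost is one model term and a somewhat wider Week 29 interval, which is the right width for that endpoint. For Cohort 2, SAP section 5 says final CFZ533 results were already given in an earlier interim report. There the change would be a re-analysis and should be labelled as one. If the reported model already contained the interaction, a statement to that effect is enough.
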